In the PROPHET trial, we intend to assess the degree of biopsy-related bleeding, measures taken to control bleeding, and potential effects of bleeding on completion of the intended procedure in 100 bronchoscopy procedures performed on single and double lung transplant recipients, randomized to prophylactic topical epinephrine versus placebo (normal saline). The study participant, physician performing the TBLB, and independent observer reviewing the procedure recording will all be blinded to the randomization. Further use of measures to control bleeding that occurs during the procedure as well as the decision to complete the procedure as planned or to abort it prematurely will be left to the discretion of the performer. In this way, we aim to elucidate a potential role of topical epinephrine in the prevention of TBLB-related airway bleeding in lung transplant recipients and assess whether the dose and volume of instillation used in our institution comprises an effective means to prevent hemorrhagic complications of TBLB.

HYPOTHESIS

We hypothesize that prophylactic instillation of topical epinephrine prior to performance of TBLB will decrease the frequency and extent of biopsy-related hemorrhage as well as result in fewer procedures being aborted earlier than intended due to bleeding complications as well as shorter overall procedure time due to the preventive effect on bleeding. Concomitantly, we hypothesize that the instillation of topical epinephrine will not be associated with a serious adverse event profile in comparison to placebo.

SPECIFIC AIMS

In this randomized-controlled double blind placebo controlled clinical trial post-lung transplant patients scheduled to receive bronchoscopy with TBLB as part of their routine standard of care will be randomized to receive a fixed dose and volume of topical endobronchial epinephrine versus matching volume of placebo which will be instilled into the target biopsy airway prior to performance of TBLB. Our study will specifically aim at providing the following information:

Aim 1: Demonstrate the feasibility of assessments of bleeding related to TBLB, including:

1. The degree of TBLB-related bleeding using a standardized grading scale used by the physician performing the procedure to quantify the degree of procedure-related bleeding.

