2. The degree of TBLB-related bleeding using a standardized grading scale used by two independent observers blinded to patient data and study drug assignment who will review a video recording of the procedure to quantify the degree of procedure-related bleeding.
3. The magnitude of inter-observer variability in grading TBLB-related hemorrhage based on review of video recording of the procedure.

Aim 2: Evaluate the hypothesis that prophylactic administration of topical epinephrine results in reductions in TBLB-related hemorrhage in lung transplant recipients, including:

1. The frequency of active measures taken to control pulmonary hemorrhage once it occurred.
2. The proportion of procedures completed as planned in terms of obtaining a predefined target number of biopsy specimens.
3. Comparison between single- and double-lung transplant recipients in terms of prevalence and degree of TBLB-related hemorrhage.
4. Identification of clinical factors associated with an increased or decreased risk of procedure-related hemorrhage.

Aim 3: Evaluate the hypothesis that prophylactic administration of topical epinephrine affects the overall efficiency of bronchoscopy with TBLB performance, including:

1. Overall duration of the bronchoscopic procedure.

2. The proportion of procedures completed as planned in terms of number of adequate biopsies obtained as assessed by the physician performing the bronchoscopy.
3. The proportion of procedures resulting in acquisition of adequate biopsy samples that allows proper pathologic evaluation of assignment of a pathologic diagnosis.

Aim 4: Explore the hypothesis that instillation of our prespecified dose and volume of topical epinephrine into the target biopsy airway is not associated with an adverse event profile that is significantly different from placebo, including:

1. The prevalence of clinically significant hemodynamic changes.
2. The prevalence of cardiac adverse events, including conduction abnormalities, arrhythmia, and myocardial ischemia.
3. The prevalence of other vascular adverse events, including stroke, mesenteric ischemia, and critical limb ischemia.
4. Identification of clinical factors associated with an increased or decreased risk of drug-related adverse events.

STUDY PROTOCOL

Overview

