 - 9.8. Date and time of scope insertion and completion of the procedure as defined by the performing bronchoscopist.
 - 9.9. Biopsy forceps brand, including outer diameter, open forceps diameter, and type of forceps (round cup, oval cup, alligator, impaling needle).
 - 9.10. Fluoroscopy time.
 - 9.11. Number of forceps passes.
 - 9.12. Total number of acquired biopsy specimens; Specimen distribution across laboratories (anatomic pathology, microbiology, other laboratory).
 - 9.13. Lobe and segment of each biopsy specimen.
 - 9.14. Any medical intervention performed in the bronchoscopy suite or in the recovery suite for stabilization of the patient’s medical condition during or following the procedure, including hemostasis, management of cardiac events, and management of respiratory events.

Outcome Measures

Primary Efficacy Outcome

The primary efficacy outcome of the PROPHET Study is the prevalence of major hemorrhage as defined by two independent reviewers who will review the procedure video while blinded to the individual patient information, study drug assignment, and any procedure related data not recorded on video. Hemorrhage will be graded according to a grading system suggested by

Pilarczyk *et al.* (43) and modified in accordance with the PROPHET Study scientific question as follows:

Grade	Description
No hemorrhage	No hemorrhage
Minor	Endobronchial hemorrhage resulting in segmental or more distal bronchus blood spillage
Intermediate	Endobronchial hemorrhage resulting in lobar bronchus blood spillage
Major	Endobronchial hemorrhage resulting in mainstem bronchus, more proximal blood spillage, or spillage into the uninvolved lung

Secondary Efficacy Outcomes

1. Occurrence of no, minor, or intermediate bleeding as defined by the independent reviewer.
2. Likert scale grading of bleeding by independent observer on a scale of 1 to 5:

1	2	3	4	5
Much less than usual for TBLB	Less than usual for TBLB	Usual for TBLB	More than usual for TBLB	Much more than usual for TBLB

3. Intra-procedural grading by the performing bronchoscopist according to procedure-related outcome as described by Ernst *et al.* and Herth *et al.* (31,44):

Grade	Description
No hemorrhage	No hemorrhage
Mild	Any bleeding originating from the biopsy target airway requiring wedging of the bronchoscope or “in and out” motion in order to achieve hemostasis

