Moderate	Any bleeding originating from the biopsy target airway requiring in addition to maneuvering the bronchoscope application of iced saline or topical epinephrine or placing the patient with the bleeding lung in the dependent position
Severe	Any bleeding originating from the biopsy target airway requiring, in addition to the above-mentioned maneuvers, early termination of the procedure or necessitating application of balloon tamponade, endotracheal intubation, application of a bronchial blocker, or use of other invasive measures to achieve hemostasis, such as bronchial artery embolization or surgical intervention

4. Number of forceps passes performed.
5. Number of adequate tissue samples obtained.

6. Early termination of the procedure due to bleeding complication, defined as non-achievement of the target number of tissue samples as designated by the performing bronchoscopist prior to the procedure related to hemorrhage.
7. Duration of the procedure from first bronchoscope insertion to last bronchoscope withdrawal.
8. Total volume of iced saline used during the procedure.
9. Total dose of unblended topical epinephrine used during the procedure.
10. Any use of hemostatic procedures including balloon tamponade, endobronchial blocker, bronchial artery embolization, emergency surgery.
11. Any use of devices or procedures with intention of securing the airway including oral airway, nasal airway, laryngeal mask, endotracheal intubation, emergency cricothyroidotomy, and emergency tracheostomy.
12. Unplanned admission to the hospital or escalation in level of care within 48 hours of the procedure.
13. Pathologic diagnosis achieved.

Safety Outcomes

The safety of topical epinephrine administration and potential instillation-related adverse events will be derived from clinical monitoring, vital signs, and ECG recordings during and immediately following the procedure as well as from any clinical, laboratory, or radiologic investigations performed during or following the procedure. Complications deemed related to topical epinephrine administration and comprise the study safety outcomes include:

1. All-cause mortality within 3 hours of instillation of the study drug.
2. Acute cardiovascular event, including cardiac arrest, new onset chest pain, acute myocardial ischemia, pulmonary edema, acute ischemic stroke, critical limb ischemia, acute mesenteric ischemia, occurring within 30 minutes of instillation of the study drug.

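### Secondary outcome 1 leaves the order of the four blinded video grades unused: depending on how it is read, it repeats the primary, splits into three tests, or becomes one unordered test

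*Combined protocol and SAP*

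**What the plan says.** Under Primary Efficacy Outcome, each video is graded none, minor, intermediate or major according to how far up the airway blood has spread. The levels are therefore ordered. The endpoint is the top level: "The primary efficacy outcome of the PROPHET Study is the prevalence of major hemorrhage as defined by two independent reviewers".

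Secondary Efficacy Outcomes, item 1, is "Occurrence of no, minor, or intermediate bleeding as defined by the independent reviewer". It does not say whether the three grades are pooled, tested one by one, or analysed together. It names one reviewer where the primary names two.

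The Hypothesis section states that the intervention "will decrease the frequency and extent of biopsy-related hemorrhage", so extent is part of the question. Other secondary outcomes also bear on extent:
- item 2, "Likert scale grading of bleeding by independent observer on a scale of 1 to 5"
- item 3, "Intra-procedural grading by the performing bronchoscopist according to procedure-related outcome"
- item 8, "Total volume of iced saline used during the procedure"
- item 9, the further topical epinephrine given

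Data Analysis sends proportions to chi-squared or Fisher's exact tests. It lists the t-test and Mann-Whitney for continuous variables and sets significance at P<0.05. It names no method for ordered categories and no multiplicity adjustment.

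**The concern.** The video grade is the trial's blinded anatomical measure of how far bleeding spread. The primary reduces it to major versus not major. That is a defensible choice, because the Hemorrhagic Complications section identifies blood reaching uninvolved airways as the main danger. Item 1 is where the rest of the scale could be used, but as worded it has no defined summary and no test that recognises that intermediate is worse than minor.

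At stake is whether this secondary outcome adds anything to the primary and, if it does, whether its result can be read in one agreed way. The plan describes a pilot meant in part to develop bleeding assessment tools and to inform later power calculations, so a settled summary of its main scale is worth having.

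**Working it through.** The plan has no power figure to reproduce: 100 procedures were chosen for feasibility. Inputs from the documents are 100 procedures, coin-toss allocation (taken as 50 per arm) and P<0.05 (taken as two-sided). Assumed: the grade distributions, a common odds ratio of 0.5, and independent procedures with one grade each.

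**Reading (a), pooled.** None + minor + intermediate = 1 − major. Take 3/50 versus 8/50 major, that is 47/50 versus 42/50 not major:
- Chi-squared = 100 × (3×42 − 8×47)² / (50×50×11×89) = 100 × 62,500 / 2,447,500 = 2.55, p = 0.110 either way.
- Fisher p = 0.1997 either way.

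Over all 2,601 possible pairs of counts (51 × 51), the two Fisher p-values agree to rounding error. The identity needs item 1 and the primary to use the same final grade.

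**Reading (b), three separate tests.** The upper bound is 3 × 0.05 = 0.15. If the tests were independent, the chance of any false positive would be 1 − 0.95³ = 0.143. The grades are dependent, so this was simulated: about 13–14% with uncorrected chi-squared and 5–9% with Fisher.

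The direction of minor is also not fixed under benefit. An odds ratio of 0.5 doubles the odds of being at or below each grade:
- Placebo 40/36/20/4%: cumulative 0.40 becomes 0.571 and 0.76 becomes 0.864, so minor falls from 36% to 29%.
- Placebo 10/20/25.5/44.5%: cumulative 0.10 becomes 0.182 and 0.30 becomes 0.462, so minor rises from 20% to 28%.

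**Reading (c), one unordered test across the grades.** Simulated error under no effect is about 4–5%, so there is no multiplicity problem. The cost is power.

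Simulated power (%), odds ratio 0.5, 20,000 runs per row:

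| Placebo none/minor/intermediate/major (%) | Rank test | Unordered four-category | None versus any, chi-squared | Major only, Fisher | Major only, chi-squared |
|---|---|---|---|---|---|
| 40/36/20/4 | 45 | 29 | 43 | 0.6 | 5 |
| 56/20/12/12 | 39 | 25 | 38 | 7 | 16 |
| 30/35/22/13 | 47 | 31 | 40 | 8 | 17 |
| 25/25/25/25 | 48 | 33 | 36 | 20 | 28 |
| 10/20/25.5/44.5 | 47 | 32 | 23 | 30 | 38 |

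The rank test's size under no effect is about 5%.

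**What drives the gain over none-versus-any.** In the table it runs from about 2 points to 24. Three further distributions separate the major rate from the no-bleeding share:
- 10/50/36/4: 43% versus 23%, a gain of 20 points with few major bleeds.
- 50/15/10/25: 42% versus 41%.
- 45/6/4.5/44.5: 43% versus 43%, no gain with many major bleeds.

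The gain is large when few procedures have no bleeding.

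**Where the ordered test loses.** If half of major bleeds become intermediate and nothing else changes, power on major (Fisher/chi-squared) against the rank test is 10/19% versus 6% at 13% major, and 28/37% versus 9% at 25% major.

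**The proposed model.** A proportional-odds model on both reviewers' grades with patient-clustered errors was simulated with 2,000 runs per setting, over 100 procedures with assumed reviewer noise. It fitted every time, with size 3.9–5.4% and 95% CI coverage 94.6–96.1%. Power was 37–45% with 100 patients and no within-patient correlation, and 25–32% with 50 patients and a latent correlation of 0.3. At 4% major, one grade was unobserved in 0.5–2.3% of runs, and the model used the remaining grades.

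**The case against.** The strongest reply is that item 1 need not be several tests. One chi-squared or Fisher test across the grades fits Data Analysis just as well, holds its error rate and gives one answer. That stands. A reader might infer that item 1 must either duplicate the primary or inflate false positives; the wording does not force that choice. Even under separate testing, the 13–14% figure belongs to chi-squared, and the plan also allows Fisher, where the rate is 5–9%. What survives under all three readings is that the order of the grades goes unused.

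An analyst might apply Mann-Whitney to the grades anyway. The plan lists it for continuous variables and words item 1 as an occurrence, so this would be a choice made at analysis.

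Extent is not neglected altogether. The iced saline volume and epinephrine dose have a named test, and the Likert score plausibly does. It would be too strong to say that the trial has no analysis of extent; the gap concerns the graded scales.

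Finally, this is a pilot, item 1 is one of 13 secondary outcomes, and every power figure rests on assumptions. All true, which limits the weight of the point. The ambiguity and the complement identity need no assumption.

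**Conclusion.** The point holds as an inexpensive improvement to one secondary outcome. No named outcome or test uses the order of the blinded video grades, and none of the three readings of item 1 repairs that. At an assumed odds ratio of 0.5 with 50 independent procedures per arm, an ordered test has about 39–48% power against about 24–33% for the unordered four-category test. The gain over none-versus-any is about 0 to 24 points.

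A reader might infer two further things that are not supported. The first is that the gain over none-versus-any grows with the rate of major bleeding. It depends mainly on the assumed share with no bleeding, as the added distributions show. The second is that the ordered test should replace the primary. It does worse than major-only testing when the drug only turns major bleeds into intermediate ones, and the plan's reason for focusing on major spillage is sound.

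The chance that minor bleeding is significantly higher on a beneficial drug is 0.4, 0.4, 1.5, 3.8 and 15.4% across the five table rows. The last value comes from the 44.5% setting. That is the highest rate in the plan's literature table, from a row listing 15 procedures with a >25 mL definition, so it should not be taken as typical. The documents give no grade distribution and no effect size, so all power figures show direction and rough size only.

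**What to change.** Keep prevalence of major hemorrhage as the primary. Replace item 1 with one prespecified ordered comparison of the four video grades (none < minor < intermediate < major):
- Fit a proportional-odds model with both reviewers' grades entered as separate observations. Do not average them, since averaging assumes equal spacing between grades.
- Cluster standard errors by patient, because Process of Obtaining Informed Consent allows a patient to contribute more than one procedure.
- Report the common odds ratio with its 95% CI, and the full grade distribution by arm.
- Use the same model for the bronchoscopist's four-level grade, with its single rating per procedure.

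The cost is one redefined secondary outcome and a sentence or two in Data Analysis. The grades are already recorded. The drawback is the lower power when only major bleeds shift to intermediate, so the result supplements the primary. Power below 50% in these settings makes it supportive evidence only. How reviewer disagreement is settled for the primary is a separate question that this change does not answer.

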7. Prior to biopsy performance 2 mL of 1:10,000 diluted epinephrine followed by 8 mL of ambient room air or 2 mL of sterile saline solution followed by 8 mL of ambient room air as described in "Study Drug and Placebo Preparation" will be instilled into the target airway by the bronchoscopist. This process may be repeated once, should the performing bronchoscopist choose to perform additional biopsy passes through a different airway. If choose to do so, the same study drug will be instilled into both airways. Any additional biopsies performed, will be done without airway instillation of study drug.
8. Biopsies will be performed using brand bronchoscopic biopsy forceps as preferred by the procedure performer. For ACR, aim will be to obtain 5 to 8 adequate biopsies, preferably from

the lateral subsegment of either the right or left lower lobes to allow optimal visualization and minimize forshortening under fluoroscopy as well as to avoid as much as possible spillage of blood into uninolved lung segments in the event of biopsy-related hemorrhage as described above. For the evaluation of radiological findings, aim will be to obtain 4 to 8 adequate biopsy specimens from an involved segment in one of the lungs based on imaging. All bronchoscopies will be performed by an experienced bronchoscopist.

9. The following data will be recorded with regard to the performance of the procedure:
 - 9.1. Patient study-arm assignment – recorded in a separate database.
 - 9.2. Indication for bronchoscopy with TBLB.
 - 9.3. Target number of TBLB specimens and target lobe and segment.
 - 9.4. Name and dosages of all medications administered to the patient in the hospital during the day of the procedure, including medications frequently administered during bronchoscopy such as topical anesthetic agents, sedation and analgesia agents, and hemostatic agents. Study drug vs. placebo administration will be recorded as described previously under “*Randomization*” and “*Study Drug and Placebo Preparation and Packaging*”.
 - 9.5. Supplemental oxygen requirements which exceed patient’s baseline requirements during or following the procedure.
 - 9.6. Any hemodynamic, cardiac, or respiratory events as recorded by telemetry in the procedure suite and/or in the recovery suite following the procedure.
 - 9.7. Bronchoscope model, including outer diameter and inner diameter of working channel.

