Data are expressed as means with standard deviations, medians with interquartile range, percentages, and proportions as appropriate. Continuous outcome variables were visually examined for normality and outliers using histograms and scatter plots. The normal distribution was assessed with the Shapiro-Wilk test. Continuous variables were compared with the Student's t-test for normally distributed data with similar variance and the Mann-Whitney tests for non-normally distributed data. Proportions were compared using Chi-squared or Fisher's exact tests as appropriate. Statistical significance was set at $P<0.05$. All statistical analyses were performed based on original assigned groups and using Stata software, version 14 (Stata Corp LLC).

Potential Benefits

We hypothesize that prophylactic instillation of topical epinephrine prior to TBLB will reduce procedure-related hemorrhage, leading to lower rate of prematurely aborted procedure due to bleeding complications and higher yield of intended biopsies. The participants may, therefore, have direct benefit from participation if prophylactic topical epinephrine reduces the rate of procedure related hemorrhage in TBLB therefore avoiding early termination of procedure and more intended biopsies taken providing a higher diagnostic yield.

No financial reimbursements or incentive for participating in the PROPHET study will be provided.

Potential Risks and Discomforts

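### The count of adequate tissue samples is compared raw although a pre-set target is recorded; adjusting for it recovers precision if targets vary

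*Combined protocol and SAP*

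**What the plan says.** Secondary Efficacy Outcomes lists item 4 as "Number of forceps passes performed" and item 5 as "Number of adequate tissue samples obtained". Both are plain counts.

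Procedure Performance, item 8, lets the intended number differ between procedures. For ACR the aim is 5 to 8 adequate biopsies. For radiological findings the "aim will be to obtain 4 to 8 adequate biopsy specimens". Item 9.3 of the same section has the team record the "Target number of TBLB specimens and target lobe and segment", and item 9.2 records the indication.

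The target is fixed in advance. Secondary outcome 6, early termination, is defined as "non-achievement of the target number of tissue samples as designated by the performing bronchoscopist prior to the procedure related to hemorrhage". Aim 2 (item 2) and Aim 3 (item 2) likewise refer to the proportion of procedures completed as planned.

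For numeric outcomes, Data Analysis offers the Student's t-test for "normally distributed data with similar variance and the Mann-Whitney tests for non-normally distributed data". It names no covariate, ratio to target or stratification. Allocation is by coin toss, not stratified by indication or target. The plan gives no power calculation for any outcome; the 100 procedures rest mainly on feasibility.

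**The concern.** Five adequate samples is a completed procedure if the target was 5 and a shortfall of three if it was 8. The raw count treats these as the same result. Any variation in the target enters the error variance of the comparison, although it is known before the study drug is instilled and cannot be affected by it.

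Randomization protects against bias from this source but does not remove the variance. With about 50 procedures per arm and a P<0.05 threshold, leaving out a recorded baseline value that partly fixes the outcome can weaken the comparison of sample counts for no saving. Coin-toss allocation also leaves chance imbalance in targets possible, and a raw comparison would not correct it.

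**Working it through.** The plan states no power figure for this outcome, so there is nothing to reproduce.

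**From the documents:** 100 procedures; permitted targets 5–8 (ACR) or 4–8 (radiological); significance level 0.05.

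**Assumed:** 50 per arm; two-sided test; independent procedures; the target distribution; the early-stopping rates; a shortfall of 1, 2, 3 or 4 samples (equally likely) when a procedure stops early; noise of −1, 0 or +1 sample (equally likely) from other causes.

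**Model:** count = target − shortfall + noise.

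**Variance components**
- Target: 2.0 if even over 4–8, 1.25 if even over 5–8, 0.25 if split between 5 and 6.
- Noise: (1 + 0 + 1)/3 = 0.667.
- Shortfall at stopping rate p: the mean shortfall given stopping is 2.5 and the mean square is 7.5, so the variance is 7.5p − (2.5p)².
  - p = 0.40 gives 2.000 and p = 0.15 gives 0.984; average 1.492.
  - p = 0.20 gives 1.250 and p = 0.05 gives 0.359; average 0.805.
  - p = 0.13 gives 0.869 and p = 0.04 gives 0.290; average 0.580.

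**Effect on the mean count:** d = 2.5 × difference in stopping rates = 0.625, 0.375 and 0.225.

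**Power:** approximately Φ(d/SE − 1.96), with SE = SD × √(2/50) = 0.2 × SD. The raw comparison carries all three components; adjustment removes the target component.

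| Stopping rates | Comparison | Variance | SE | d/SE | Power |
|---|---|---|---|---|---|
| 40% v 15% | raw, targets 4–8 | 4.159 | 0.408 | 1.53 | 33% |
| | raw, targets 5–8 | 3.409 | 0.369 | 1.69 | 39% |
| | raw, targets 5 or 6 | 2.409 | 0.310 | 2.01 | 52% |
| | target removed | 2.159 | 0.294 | 2.13 | 57% |
| 20% v 5% | raw, targets 4–8 | 3.471 | 0.373 | 1.01 | 17% |
| | raw, targets 5–8 | 2.721 | 0.330 | 1.14 | 21% |
| | raw, targets 5 or 6 | 1.721 | 0.262 | 1.43 | 30% |
| | target removed | 1.471 | 0.243 | 1.55 | 34% |
| 13% v 4% | raw, targets 4–8 | 3.247 | 0.360 | 0.62 | 9% |
| | target removed | 1.247 | 0.223 | 1.01 | 17% |

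**Simulation under the same assumptions**, raw t-test against a linear model with target as covariate:
- Targets even over 4–8: 33% v 55% at 40% v 15%, and 16% v 32% at 20% v 5%.
- Targets 5 or 6: 53% v 57%, and 28% v 31%.

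The closed form agrees within about three points.

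**Type I error:** with equal stopping rates of 10%, the raw tests rejected in 4.6% to 5.1% of runs and the target-adjusted model in 4.4% to 4.5%.

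**Choice of adjusted analysis:** at 40% v 15% with targets over 4–8, Mann-Whitney power rose from about 30% on raw counts to about 48% on obtained minus target. That is a real gain, but less than the linear model gives.

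**Forceps passes:** no calculation was made. The target counts adequate specimens, and passes also depend on yield per pass, for which the documents give no figure.

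**The case against.** The strongest reply is that the completion question does not depend on this count. Item 6 and Aims 2 and 3 (item 2 of each) already judge completion against plan. In simulation, Fisher's exact test on bleeding-related early termination had about 73% power at 40% v 15% and 51% at 20% v 5%, taking the stopping flag as correctly recorded. With noise present, that beats the adjusted count. This stands: a reader might infer that the plan cannot detect an effect on biopsy completion, and the documents do not support that. Item 6 is, however, binary and limited to shortfalls related to hemorrhage. It does not say how many samples were lost or capture shortfalls from other causes, so outcome 5 still deserves an efficient analysis if it is kept.

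A second reply is that the assumed effects are generous. The transplant studies tabulated under Sample Size and Power Calculations report clinically significant bleeding of 0.5% to 13%, apart from one small study at 44.5%. Stopping early for bleeding may well be rarer. At 13% v 4% neither analysis is informative (9% and 17%). This also stands, and it limits what adjustment can achieve.

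Third, this concerns two of 13 secondary outcomes in a pilot. That bears on priority but gives no reason to omit a covariate already collected.

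**Conclusion.** The point holds as a loss of precision for outcome 5. If targets spread evenly over 4 to 8, adjustment raises power by about 22 points at 40% v 15% stopping (55% − 33%) and about 16 points at 20% v 5% (32% − 16%). If they cluster at 5 or 6, the gain is about 3 to 4 points. If all targets are equal, there is none. These figures rest on an assumed target distribution, stopping rates, shortfall and noise, and on independent procedures.

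Three stronger readings are tempting and are not supported:
- That target variation swamps the treatment effect. The documents give a permitted range, not the actual spread, and no effect size.
- That the raw comparison is biased. The target is set before instillation by a blinded operator, allocation is random, and type I error stays near 5%.
- That forceps passes should be analysed as passes minus target. The target is for specimens, so that difference has no clear meaning.

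The primary outcome is unaffected.

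**What to change.** In Data Analysis, specify that adequate samples will be analysed by linear regression on arm, with the recorded pre-procedure target and the indication as covariates. Obtained minus target is an acceptable simpler alternative. Show raw counts by arm descriptively.

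For forceps passes, use the recorded target and indication as covariates only, and expect a smaller gain.

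The cost is a few sentences of analysis text. Target and indication are already recorded under items 9.3 and 9.2, so no new data, procedures or participants are needed.
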